## 11 SAFETY

The Investigator is responsible for monitoring the safety of patients enrolled in this study.

If the patient is withdrawn from treatment, the patient will discontinue study treatment and on that day or as soon as possible thereafter undergo an EoT visit and have the Follow-up Period EoS visit scheduled (see Section 9.4).

## 11.1 Pregnancy

CCI		

## **11.2** Adverse Events

The Investigator is responsible for monitoring the safety of patients who have enrolled in the study and for accurately documenting and reporting information as described in this section. Patients will be instructed to report to the Investigator any AE that they experience. Investigators will ask about the occurrence of AEs at each visit. Investigators are required to document all AEs occurring during the clinical study, commencing with the first dose of bomedemstat at the Transition Visit through to the EoS Visit (scheduled at 14 days post last bomedemstat dose). AE recording will continue for patients who discontinue study drug but remain in Follow-up Period, until their EoT and EoS Visits have been completed.

Note: Any medical event i.e., (S)AE which is ongoing from the feeder protocol study at the time of dosing with bomedemstat in this protocol must be documented in the patient's medical notes and will be recorded on the appropriate eCRF pages as AEs ongoing at the time of study entry.

New AEs will be recorded on designated eCRF pages. Each AE is to be characterised (i.e., verbatim term) and information provided regarding its seriousness, start and stop dates, intensity, outcome, and causal relationship with the study drug.

An AE is any undesirable physical, psychological or behavioral effect experienced by a patient during participation in an investigational study, in conjunction with the use of the drug or biologic, whether or not product-related. This includes any untoward signs or symptoms experienced by the patient from the time of first dose with bomedemstat under this protocol until completion of the study.

AEs may include, but are not limited to:

- Subjective or objective symptoms spontaneously offered by the patient and/or observed by the Investigator or medical staff
- Findings at physical examinations
- Laboratory abnormalities of clinical significance
- Overdose defined as any dose exceeding the prescribed dose for bomedemstat

• Potential DILI events defined as an elevated AST or ALT laboratory value that is greater than or equal to 3× the ULN and an elevated total bilirubin laboratory value that is greater than or equal to 2× the ULN and, at the same time, an alkaline phosphatase laboratory value that is less than 2× the ULN, as determined by way of protocol-specified laboratory testing or unscheduled laboratory testing.

It is important Investigators record accurate AE terms in the eCRFs. Wherever possible, a specific disease or syndrome rather than individual associated signs, symptoms or laboratory parameter will be identified by the Investigator and recorded in the eCRF. However, if an observed or reported sign, symptom or laboratory parameter is not considered a component of a specific disease or syndrome by the Investigator, or is atypical, it should be recorded as a separate AE in the eCRF.

Disease signs, symptoms, and/or laboratory abnormalities already existing prior to the use of the study drug are not considered AEs after treatment unless they reoccur after the patient has recovered from the preexisting condition or in the opinion of the Investigator they represent a clinically significant exacerbation in intensity or frequency.

Clinical significance is defined as any variation in signs, symptoms, or testing that has medical relevance and may result in an alteration in medical care. The Investigator will continue to monitor the patient until the assessment returns to Baseline or until the Investigator determines that follow-up is no longer medically necessary.

## 11.2.1 Adverse Event Intensity

AE intensity will be evaluated using the NCI CTCAE version 5, published 27-NOV-2017. For AEs not included in the NCI CTCAE, the Investigator will be required to assess the intensity of the adverse drug/biologic experience using the following categories and associated guidelines:

Grade	Guideline
1	Mild; asymptomatic or mild symptoms; clinical or diagnostic observations only; intervention not indicated
2	Moderate; minimal, local or noninvasive intervention indicated; limiting age-appropriate instrumental $\mbox{\rm ADL}^*$
3	Severe or medically significant but not immediately life-threatening; hospitalization or prolongation of hospitalization indicated; disabling; limiting self-care ADL**
4	Life-threatening consequences; urgent intervention indicated
5	Death related to AE

Note 1: A semi-colon indicates 'or' within the description of the grade.

Note 2: Activities of Daily Living (ADL)

\*Instrumental ADL refer to preparing meals, shopping for groceries or clothes, using the telephone, managing money, etc.

\*\*Self-care ADL refer to bathing, dressing and undressing, feeding self, using the toilet, taking medications, and not bedridden.

#### 11.2.2 Adverse Event Relatedness

The Investigator will make a judgment regarding whether or not, in his/her opinion, the AE was related to study drug. The Investigator will also evaluate any changes in laboratory values, make a determination as to whether the change is clinically significant, and whether or not the change(s) were related to study drug. However, even if the Investigator feels there is no relationship to the study drug, the AE or clinically significant laboratory abnormality MUST be recorded in the eCRF. Below are guidelines for relationship assessment:

- Unrelated: There was no relationship of the AE to the use of the drug or biologic. This may include, but is not limited, to the adverse experience being an expected outcome of a previously existing or concurrent disease, concomitant medication or procedure the subject experienced during their treatment period.
- Remote/Unlikely: AEs which are judged probably not related to the drug or biologic.
- Possible: There was no clear relationship of the AE to the use of the drug or biologic; however, one cannot definitively conclude that there was no relationship.
- Probable: While a clear relationship to the drug or biologic cannot be established, the event is associated with an expected AE (per the current Investigator Brochure or SAB findings) or there is no other medical condition or intervention which would explain the occurrence of such an experience.
- Definite: The relationship of the use of the drug or biologic to the experience is considered definitively established.

If a causal relationship is considered probable, possible, or definite by the Investigator or Sponsor (dependent on the regional reporting requirements), the AE is considered to be "related" for purposes of regulatory reporting. If a causal relationship is considered remote/unlikely or unrelated, the AE is considered "unrelated" for purposes of regulatory reporting.

#### 11.2.3 Serious Adverse Events

SAEs will be reportable from the time of first dose in the extension study through the EoS or ET Visit **or** until the Investigator and sponsor determine that follow-up is no longer necessary. SAEs that are suspected to be drug related will be reported even if they occur when the patient is no longer on the study.

An SAE is any AE that results in any of the following outcomes:

#### Death

**Life-threatening experience**. Any AE that places the patient, in the view of the reporter, at immediate risk of death from the AE as it occurred, i.e., does not include an AE that had it occurred in a more severe form, might have caused death.

**Required or prolonged inpatient hospitalization**\*. The AE resulted in an initial inpatient hospitalization or prolonged an existing hospitalization of the patient. If a patient is hospitalized as part of the clinical use of the product, a period of normal hospitalization will be outlined in the

Imago BioSciences, Inc., a subsidiary of Merck & Co., Inc. Bomedemstat (IMG-7289/MK-3543)

protocol or by the judgment of the Investigator. Hospitalizations longer than this period will be prolonged hospitalizations.

**Persistent or significant disability/incapacity**. An AE that resulted in a substantial disruption of a person's ability to conduct normal life functions.

**Congenital Anomaly.** The exposure of the patient to the drug or biologic during pregnancy that is judged to have resulted in the congenital anomaly/birth defect.

**Important medical events**. AEs that may not result in death, be life-threatening, or require hospitalization may be considered an SAE when, based upon appropriate medical judgment, may jeopardise the patient or subject and may require medical or surgical intervention to prevent one of the outcomes listed above. Important medical events or interventions may be considered an SAE based upon medical judgment of the Investigator.

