repressor (GFI1) and RE-1 silencing transcription factor (REST), recruit LSD1 to specific genomic locations (Metzger *et al.*, 2005; Saleque *et al.*, 2007; Lin *et al.*, 2010). LSD1 is part of a larger protein complex, containing, e.g., Co-RE-1 silencing transcription factor (CoREST) or nucleosome remodeling and histone deacetylase (NuRD), which dictates the cell- and site-specific chromatin remodeling (Lee *et al.*, 2005; Foster *et al.*, 2010). These complexes may also include DNA methyltransferase 1 (DNMT1) and histone deacetylases 1, 2 and 3 (HDAC1, 2, and 3) activities all of which contribute to maintaining or modifying the epigenetic state at that specific genomic site (Shi *et al.*, 2005; Orkin and Hochedlinger, 2011). Thus, an important property of LSD1 beyond its own enzymatic activity is its function as a scaffold for other proteins and epigenetic enzymes that are co-recruited to genomic sites. Likewise, LSD1 bound to specific sites precludes the binding of other factors that may influence transcription.

LSD1 is unique among the many histone demethylases in that it coordinates flavin adenine dinucleotide (FAD) to oxidatively remove one or two methyl groups, in the process producing  $H_2O_2$  and formaldehyde. As such, FAD is an essential co-factor for LSD1 activity (Shi *et al.*, 2004). The other 34 histone lysine demethylases, collectively termed the Jumonji demethylases, employ an iron-dependent mechanism to remove methyl groups from histone lysines (Klose *et al.*, 2006).

LSD1 is an essential gene; loss of LSD1 activity leads to early embryonic lethality (Wang et al., 2009; Foster et al., 2010). The protein is also needed for regulating the balance between self-renewal and proliferation (Wang et al., 2007). A conditional in vivo LSD1 knockdown (KD) using a doxycycline-inducible short hairpin LSD1 (shLSD1) established LSD1 as a central regulator of hematopoietic stem cells (HSCs) and progenitor cells (Sprussel et al., 2012). An inducible LSD1 KD resulted in profound but reversible thrombocytopenia, neutropenia and anemia; monocyte numbers were increased as monopoiesis does not require LSD1 activity. LSD1 KD for 27 days led to an increase in circulating multipotent progenitors (MPPs) and HSCs with a concomitant down-regulation of chemokine (C-X-C motif) receptor 4 (CXCR4) without affecting the size of the quiescent long-term HSC pool (Sprussel et al., 2012).

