#### 6.1.2 Exclusion Criteria

[figure not shown]
Patients will be excluded from the study if they meet any of the following criteria:

- 1. Ongoing participation in another investigational study (except observational studies).
- 2. A history of non-compliance in a prior bomedemstat study (excluding dose suspensions that were medically warranted).
- 3. Current use of a prohibited medication (e.g., romiplostim).
- 4. Medical, psychiatric, cognitive, or other conditions that, in the Investigator's opinion,

compromise the patient's safety, ability to give informed consent, or comply with the trial protocol.

5. Females who are pregnant or breastfeeding or plan to become pregnant or breastfeed during the study.

**Note:** In the UK, male patients with a pregnant partner must agree to use a condom to avoid exposure to the developing child.

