## 11.2.4 Reporting Serious Adverse Events

SAEs will be reported promptly, using the SAE Report Form, once the Investigator determines that the event meets the protocol definition of an SAE. The Investigator or designee will report the SAE within 24 hours of his/her becoming aware of these events regardless of relationship of the SAE to the use of study drug, in accordance with the instructions in the Study Reference Manual. The Investigator will always provide an assessment of relatedness at the time of the initial report as described in Section 11.2.2. The SAE Report will always be completed as thoroughly as possible with all available details of the event within the designated time frames. Copies of relevant patient records, autopsy reports, and other documents may be requested.

If the Investigator does not have all information regarding an SAE, he/she will not wait to receive additional information before reporting the SAE. The SAE Report will be updated when additional information is received **within 24 hours of receipt of such information**.

**Important:** For fatal and life-threatening events, the event should be reported in the EDC system immediately or within 24 hours of learning of the event. A death occurring during the study or information related to such occurrence that comes to the attention of the Investigator during the study must be reported immediately to the Sponsor. A detailed SAE reporting procedure and contact information will be included in the Study Reference Manual (SRM) and provided to the site before any patients are consented.

Additionally, the Institutional Review Board (IRB), Independent Ethics Committee (IEC) and Human Research Ethics Committee (HREC), as applicable, must be notified in writing of any SAEs that require expedited reporting to Regulatory Authorities. Depending upon regional requirements, it is the responsibility of the Investigator to notify the IRB/IEC/HREC. All SAEs meeting expedited reporting requirements will be reported to appropriate regulatory agencies by sponsor or their designee as soon as possible and within the timeframes specified in the various regions in which the study is to be conducted.

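### Section 11.2.3 makes a drug-causality judgement part of the congenital-anomaly seriousness criterion, and names only the patient's own exposure

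*Combined protocol and SAP*

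**What the plan says.** Section 11.2.3 opens its list of seriousness criteria with "An SAE is any AE that results in any of the following outcomes". The congenital-anomaly entry then reads "The exposure of the patient to the drug or biologic during pregnancy that is judged to have resulted in the congenital anomaly/birth defect".

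Four other places bear on it:

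- **Section 11.2 (AE definition).** "An AE is any undesirable physical, psychological or behavioral effect experienced by a patient during participation in an investigational study", and this holds "in conjunction with the use of the drug or biologic, whether or not product-related".
- **Section 11.2.2 (relatedness).** The investigator rates causality separately on five levels. Possible, probable and definite count as related for regulatory reporting.
- **Section 11.2.4 (reporting).** SAEs go to the sponsor within 24 hours "regardless of relationship of the SAE to the use of study drug". This applies once the investigator has decided that the event satisfies the protocol's SAE definition.
- **Section 11.2.3 (reporting period).** SAEs are reportable to the EoS or ET visit or, as a stated alternative, for as long as the investigator and sponsor consider follow-up needed. In addition, "SAEs that are suspected to be drug related will be reported even if they occur when the patient is no longer on the study".

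Section 11.1 (Pregnancy) is present but its content is redacted.

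**The concern.** Seriousness describes what happened, and relatedness describes what is thought to have caused it. The protocol keeps the two apart almost everywhere, and Section 12.4.1 lists seriousness and causality as separate attributes of AEs under the primary safety endpoint. The congenital-anomaly entry merges them. A case counts under that entry only after someone has concluded that the drug was responsible, so cases are selected on the answer that the safety data are meant to inform.

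Reproductive harm is not a remote topic for this drug. Section 3.2 says that "loss of LSD1 activity leads to early embryonic lethality", and Section 3.4 describes bomedemstat as an irreversible LSD1 inhibitor. Section 6.1.2 also recognises exposure through a male patient: in the UK, "male patients with a pregnant partner must agree to use a condom to avoid exposure to the developing child". The seriousness criterion does not follow that route.

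**Working it through.** The protocol gives no figure that bears on this point and no arithmetic applies. The check is a reading of the sections side by side.

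**Step 1. Is causality required by the other criteria in Section 11.2.3?** No. Death, life-threatening experience, hospitalisation and disability are each defined by what happened to the patient. Important medical events rest on medical judgement of jeopardy and the need for intervention. None asks whether the drug was the cause. Only the congenital-anomaly entry does.

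**Step 2. Does the entry name an outcome?** Not directly. The list is introduced as outcomes, but the grammatical subject of this entry is the exposure, and the defect appears only as its judged consequence.

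**Step 3. Does Section 11.2.4 repair it?** No. Its indifference to relationship begins after the SAE definition is met. A defect judged unrelated has already failed the congenital-anomaly criterion, so the rule does not reach it by this route.

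**Step 4. Which cases meet the criterion as worded?**

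| Case | Meets the congenital-anomaly criterion? |
|---|---|
| Female patient exposed in pregnancy, defect judged caused by drug | Yes |
| Same, relatedness rated possible | Unclear: the entry does not say which level of the Section 11.2.2 scale amounts to its causal judgement |
| Same, rated remote/unlikely or unrelated | No |
| Child of a male patient, any rating | No on the natural reading, since the exposure named is the patient's during pregnancy |

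In the last row, one could strain to count a man's own dosing during his partner's pregnancy. The causality condition would still apply.

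**Step 5. Would rewording the entry be enough?** No. An SAE must first be an AE, and Section 11.2 defines an AE as an effect experienced by a patient. A defect in a child, most plainly a partner's child, is not such an effect. The definitions have to be changed together.

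**The case against.** The strongest reply is that the entry is one line in a reporting system that cannot be seen in full. Section 11.1 is redacted and is where pregnancies, partner pregnancies and birth outcomes would be expected. Section 11.2.5 mentions other reportable safety events alongside AEs and SAEs, and Section 11.2.4 places the detailed SAE procedure in the Study Reference Manual. The important-medical-event criterion has no causality condition. All of this stands as a limit on what may be concluded, although the last route is discretionary and speaks of jeopardy to the patient or subject, not to a child.

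A second reply is that Sections 11.2.3 and 11.2.4 do not strictly contradict each other, because a narrow definition can coexist with a broad reporting rule. That is correct. The conflict is with the rule's intent, not with its letter.

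A reader might infer three stronger things that the documents do not support:

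- **That these birth defects are not SAEs at all.** The visible text shows only that they do not meet this one criterion.
- **That births fall outside the SAE window because EoS is 14 days after the last dose, leaving only events suspected to be related.** Section 11.2.3 allows reporting to continue beyond EoS without a causality condition, so there is no strict cutoff. A partner's pregnancy may also run its course while a male patient is still on treatment.
- **That almost no unattributed cases would be captured or reach the Safety Advisory Board.** No capture rate can be derived while Section 11.1 is unseen.

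The mechanism argument also has a limit. Section 3.2 describes early embryonic loss, which neither the present entry nor a reworded birth-defect entry would record. It shows why reproductive outcomes matter here, not how often a birth defect should be expected.

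**Conclusion.** The criterion is wrong as written. It makes a drug-causality judgement a condition of seriousness and names only the patient's own exposure, so a defect judged unrelated, or one in a male patient's child, does not meet it. The first half is the firmer, since it rests on plain wording that differs from every other entry in the list. The male-patient half is weaker in consequence, because the redacted section may provide for it.

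Severity is minor. Enrolment is about 80 (Section 6.2), pregnancy and planned pregnancy are exclusions (Section 6.1.2), and women of childbearing potential have serum pregnancy tests, so few events are expected. The conclusion does not depend on what Section 11.1 says. If that section is causality-neutral, the entry in Section 11.2.3 is inconsistent with it; if it is not, the entry's gap is left open. The wording needs correcting in both cases.

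**What to change.** 1. In Section 11.2.3, replace the entry with an outcome: *Congenital anomaly or birth defect in the offspring of a patient (female, or male through a partner), whatever the judged cause.*
2. In Section 11.2 or 11.2.3, state that this outcome counts as a reportable event although the AE definition refers to effects experienced by a patient. Without this sentence a partner's child still fails the opening condition of the SAE definition.
3. Reconcile the new wording with Section 11.1, with the reporting period in Section 11.2.3 (saying how such an outcome is reported if it becomes known after EoS) and with Section 11.2.4. Relatedness continues to be rated separately under Section 11.2.2.

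The cost is one definition, one or two reporting sentences and a matching change to the SAE form. The downside is an occasional extra SAE report and follow-up of a pregnancy outcome.

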## 11.2.4 Reporting Serious Adverse Events

SAEs will be reported promptly, using the SAE Report Form, once the Investigator determines that the event meets the protocol definition of an SAE. The Investigator or designee will report the SAE within 24 hours of his/her becoming aware of these events regardless of relationship of the SAE to the use of study drug, in accordance with the instructions in the Study Reference Manual. The Investigator will always provide an assessment of relatedness at the time of the initial report as described in Section 11.2.2. The SAE Report will always be completed as thoroughly as possible with all available details of the event within the designated time frames. Copies of relevant patient records, autopsy reports, and other documents may be requested.

If the Investigator does not have all information regarding an SAE, he/she will not wait to receive additional information before reporting the SAE. The SAE Report will be updated when additional information is received **within 24 hours of receipt of such information**.

**Important:** For fatal and life-threatening events, the event should be reported in the EDC system immediately or within 24 hours of learning of the event. A death occurring during the study or information related to such occurrence that comes to the attention of the Investigator during the study must be reported immediately to the Sponsor. A detailed SAE reporting procedure and contact information will be included in the Study Reference Manual (SRM) and provided to the site before any patients are consented.

Additionally, the Institutional Review Board (IRB), Independent Ethics Committee (IEC) and Human Research Ethics Committee (HREC), as applicable, must be notified in writing of any SAEs that require expedited reporting to Regulatory Authorities. Depending upon regional requirements, it is the responsibility of the Investigator to notify the IRB/IEC/HREC. All SAEs meeting expedited reporting requirements will be reported to appropriate regulatory agencies by sponsor or their designee as soon as possible and within the timeframes specified in the various regions in which the study is to be conducted.

